6.0 Analysis and Reporting

6.1 Interim Reports and Trend Analysis

Interim reports will be submitted to FDA every 6 months for the first 2 years and yearly thereafter.

The observed number of enrollments in the study and the sub-study at participating centers, number of implants at participating centers and number of overall US implants will be included in the progress reports until enrollment is completed.

Other data summarized in the progress reports will include:

- Demographic data including gender, age, NYHA functional classification, left ventricular ejection fraction, and indication for device. Continuous variables will be summarized by average and standard deviation. Categorical variables will be summarized by frequency and percentage
- Complications and observations related to the Optisure RV lead will be summarized and reported
- Complications or observations that are unrelated to the RV lead (shown in Table 2) will be summarized and reported
- Signal amplitude measurements for Optisure leads at implant/enrollment, as appropriate, and at each follow-up visit (if available) will be summarized and reported.
- Capture thresholds for Optisure leads at implant/enrollment, as appropriate, and at each follow-up visit will be summarized and reported.

- Pacing lead impedance for Optisure leads at implant/enrollment, as appropriate, and at each follow-up will be summarized and reported.
- High voltage lead impedance for Optisure leads at implant/enrollment, as appropriate, and at each follow-up will be summarized and reported.
- The rate of successful Optisure RV lead implants will be reported (only applicable to patients enrolled at or before implant)
- Total implant procedure time (skin to skin) – the average and standard deviation for successful Optisure lead implants will be reported (only applicable to patients enrolled at or before implant)
- Implant approach (site of venous access) (only applicable to patients enrolled at or before implant)
- Percentage of leads with externalized conductors, other visual lead anomalies at different time points (24, 36, 48 and 60 months)
- Type, location and extent of externalized conductors and other visual lead anomalies
- Percentage of leads with electrical dysfunction in the sub-study
- Prevalence of “other insulation anomalies” in returned Optisure leads

Table 2: Complications or Observations That Are Unrelated To the RV Lead

Pneumothorax
Lead dislodgement occurring in the peri-operative period (within 30 days of implant)
Elevated pacing thresholds due to patient physiology
Loss of capture unrelated to lead fracture or dislodgement
Loss of sensing unrelated to lead fracture or dislodgement
Oversensing due to a change in patient physiology
Undersensing due to a change in patient physiology
Generator malfunction
Abnormal lead pacing impedance ($\leq 200 \Omega$ or $\geq 2000 \Omega$) unrelated to lead fracture or dislodgement
Abnormal lead defibrillation impedance ($\leq 20 \Omega$ or $\geq 100 \Omega$) unrelated to lead fracture or dislodgement
Failure to detect VT/VF due to a cause unrelated to the Optisure RV lead
Complications related to other implanted leads (right atrial or left ventricular)

A trend analysis for the complications listed in Table 1 will be summarized by quarter with the first analysis carried out after 100 patients have been enrolled and followed for a minimum of 6 months. Each interim report will include a plot of quarterly trend analyses of % of Patients with Complications and # of Complications/patient-year from all preceding analyses.

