- **Lead Fracture:** A break in a conduction cable or coil of a pacing or defibrillation lead typically evidenced by an increase in impedance, intermittent or complete loss of capture, intermittent or complete loss of sensing, noise on the intra-cardiac electrogram and rarely, by visual signs of conductor coil fracture on x-ray.
- **Lead Insulation Damage:** A disruption to the integrity of the lead insulation without disruption of the conductor cable(s) or coil observed visually, electrically, or radiographically. An insulation break may be indicated by a drop in impedance, and can cause loss of capture or high voltage therapy delivery or sensing problems.
- **Loss of Capture:** The inability of the device's output pulse to result in depolarization and contraction of the appropriate cardiac chamber. Causes include insufficient stimulus strength, separation of the electrode from the myocardium, some anti-arrhythmic medications and placement of the stimulating electrode in contact with a non-responsive portion of the myocardium such as scar tissue. Delivery of an output pulse at a time when the myocardium is physiologically refractory is not loss of capture, since capture is not physiologically feasible.
- **Loss of Sensing:** A condition in which the pulse generator is unable to sense intrinsic cardiac signals (applicable to RA and RV leads).

- **Observation:** Adverse events that can be managed without invasive intervention (e.g., oversensing or loss of pacing capture, which is remedied by reprogramming of the pulse generator).
- **Oversensing:** The detection of inappropriate electrical signals by the pulse generator's sense amplifier. These signals, such as myopotentials, electromagnetic interference, T waves or crosstalk between atrial and ventricular channels, must be of sufficient duration to interfere with normal device function (applicable to RA and RV leads).
- **Pneumothorax:** An accumulation of air in the pleural cavity due to a disruption of the pleural lining.
- **Re-Attempted Implant:** Implant is being re-attempted in a new procedure due to previous failed implant of the Optisure lead
- **Re-Implant:** Implant is being attempted in a new procedure because of a previous removal of the Optisure lead implanted at enrollment, e.g. due to infection.
- **Successful implant:** An Optisure lead is implanted.

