5.0 Study Outcome Measures

5.1 Primary Outcome Measure

5.1.1 Freedom from RV Lead Related Complications

The primary outcome measure for the Optisure Lead Post Approval study is the complication free survival rate at 5 years for complications related to the Optisure RV leads.

The hypothesis is as follows:

H0: Complication free survival at 5 years \leq 92.5%

H1: Complication free survival at 5 years $>$ 92.5%

The desired outcome is to reject the null hypothesis. The null hypothesis will be rejected at the 5% significance level if the 95% Lower Confidence Bound (LCB) for the freedom from complications is greater than 92.5%.

Sample Size

Assuming that the time to first complication follows an exponential distribution and the complication-free survival at 5 years is 95%, a sample size of 645 patients provides 80% power to reject the null hypothesis of 92.5% complication-free survival years at the 5% significance level (See Appendix D for detailed sample size calculations).

Patient Group

All patients who had an attempted implant of the Optisure RV lead will be included in the analysis of this endpoint.

Analysis

All complications will be classified as related to the Optisure RV lead or unrelated.

The following complications will be included in this analysis:

- Cardiac perforation
- Lead dislodgement that occurred greater than 30 days after implant
- Lead insulation damage
- Lead fracture
- Abnormal RV lead performance (abnormal lead defibrillation impedance, abnormal lead pacing impedance, elevated pacing thresholds, loss of capture, failure to deliver therapy, loss of sensing, oversensing, undersensing)

- Other unexpected complications that are considered related to the RV lead

The survival time for all patients will be calculated as the number of days from implant or attempted implant to the date the complication was first discovered. For patients who do not experience a complication related to the Optisure RV lead at the time of their withdrawal, the survival time will be censored on the date of their withdrawal. For patients who have not experienced any complication related to the Optisure RV lead at the time of analysis, the survival time will be censored on the date of analysis. The endpoint will be evaluated using the Kaplan-Meier method and the 95% lower confidence bound (LCB) will be obtained by transformation from its log scale, based on Peto et al¹. The null hypothesis will be rejected if the 95% LCB is greater than 92.5%.

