5.2 Secondary Outcome Measures

5.2.1 Optisure Lead-Related Complication Rates

The objective is to characterize the complication rate of the Optisure lead, and to perform a trend analysis of all complications. All complications will be evaluated for their relationship to the RV lead, reported and summarized.

The following complications will be reported as related to the RV lead:

- Cardiac perforation
- Lead dislodgement that occurred greater than 30 days after implant
- Lead insulation damage
- Lead fracture
- Abnormal RV lead performance (abnormal lead defibrillation impedance, abnormal lead pacing impedance, elevated pacing thresholds, loss of capture, failure to deliver therapy, loss of sensing, oversensing, undersensing)
- Other unexpected complications that are considered related to the RV lead

Table 1: Summary of RV Lead Related Complications

Description of Complication	Number of Patients with Comp (No. of pts = X)	% of Patients with Comp	Number of Comps	# Comps/pt-years (Total pt-years =)
Cardiac perforation	X	X%	X	X
Lead dislodgement that occurred greater than 30 days after implant	X	X%	X	X
Lead insulation damage	X	X%	X	X
Lead fracture	X	X%	X	X
Abnormal RV lead performance	X	X%	X	X
Other unexpected complications that are considered related to the RV lead	X	X%	X	X
Total	X	X%	X	X

Sample Size

The sample size required to obtain a two-sided 95% upper confidence limit for the complication rate of no more than 5%, based on the Clopper-Pearson exact Binomial method², assuming an expected complication rate of 3.5%, is 828 patients (See Appendix D for detailed sample size calculations).

Sample size accounting for patient attrition

The following categories are included to account for patient attrition.

1. Unsuccessful Implant

A small proportion of the patients are expected to have an unsuccessful implant of the Optisure lead (less than 1%).

2. Mortality

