5.2.2 Optisure Lead Related Events

Adverse Events related to the Optisure lead will be classified and reported as complications or observations. RV lead related complications or observation are defined in section 5.2.1

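### Four Table 2 rows use a narrower test for unrelated to the RV lead than the endpoint sections do, so some lead-caused complications fit both lists

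*Protocol*

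**What the plan says.** Section 5.1.1 makes relatedness the first step: "All complications will be classified as related to the Optisure RV lead or unrelated". It then lists the event types that count, among them "Abnormal RV lead performance (abnormal lead defibrillation impedance, abnormal lead pacing impedance, elevated pacing thresholds, loss of capture", followed by further items including loss of sensing. No cause is attached to these items. Section 5.2.1 gives the same list under the words "The following complications will be reported as related to the RV lead", and section 5.2.2 adds that "RV lead related complications or observation are defined in section 5.2.1". Section 11.0 defines an RV lead related complication simply as one that is related to the RV lead.

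Section 6.1 provides for the other side: "Complications or observations that are unrelated to the RV lead (shown in Table 2) will be summarized and reported". The title of Table 2 covers complications as well as observations. Two of its rows read "Loss of capture unrelated to lead fracture or dislodgement" and "Loss of sensing unrelated to lead fracture or dislodgement". The rows for abnormal pacing impedance and abnormal defibrillation impedance carry the same condition.

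The definition of lead insulation damage in section 4.2 excludes disruption of the conductor and states: "An insulation break may be indicated by a drop in impedance, and can cause loss of capture". It goes on to name high-voltage therapy delivery and sensing problems.

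**The concern.** Not being caused by fracture or dislodgement is a weaker condition than not being caused by the lead. Table 2 therefore takes in some events that the endpoint sections would call lead related. The primary analysis is a single-arm test against a fixed 92.5%, so each related or unrelated call enters the result directly, with no control arm to absorb a classification habit. The same calls fill Table 1, which feeds the quarterly trend analysis (6.1) and the final-report proportions (6.2). Any error has one direction: applying the Table 2 wording can only take events out, which raises the apparent complication-free rate.

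**Working it through.** **Text comparison**

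| Finding | 5.1.1 and 5.2.1 | Table 2 puts it under unrelated when |
|---|---|---|
| Loss of capture | counted, no cause stated | fracture or dislodgement is not the cause |
| Loss of sensing | counted, no cause stated | same |
| Abnormal pacing impedance | counted, no cause stated | same |
| Abnormal defibrillation impedance | counted, no cause stated | same |
| Elevated thresholds, oversensing, undersensing | counted, no cause stated | the patient's physiology is the cause |
| Failure to detect VT/VF | not named | the cause lies outside the Optisure RV lead |

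The last two rows are compatible with a plain relatedness judgement; the first four are not. Fracture and late dislodgement already have their own bullets in 5.1.1, and dislodgement within 30 days is itself a Table 2 row. Under the Table 2 wording the four findings would thus add almost nothing to the abnormal-performance category. Insulation damage and perforation also have their own bullets. What remains in the overlap is an event of the four types that was treated invasively and caused by the lead, with no fracture, dislodgement, insulation damage or perforation confirmed.

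**Reproducing the plan's figure (N=645)**

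Inputs: null 92.5%, assumed freedom 95%, and a one-sided 95% bound (the Appendix D code sets conf.int=0.9), Peto standard error, log-log transform as in that code. With no censoring before 5 years the bound depends only on the number of events x:

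- S = 1 − x/N; n = N − x + 1; SE = √((1 − S)/n)
- LCB = exp(−exp(ln(−ln S) − 1.645·SE/ln S))
- x = 37: S = 0.9426, n = 609, SE = 0.00971, LCB = 0.9255, which passes
- x = 38: S = 0.9411, n = 608, SE = 0.00984, LCB = 0.9238, which fails

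H0 is rejected with 37 or fewer events. P(X ≤ 37) for Binomial(645, 0.05) is 82.9%; Appendix D prints 0.8324. The figure reproduces.

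**Illustration: an assumed share f of events is moved to unrelated**

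The counted event probability becomes p(1 − f), and the chance of rejection is P(X ≤ 37).

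| True freedom | f = 0 | f = 10% | f = 20% |
|---|---|---|---|
| 92.5% (p = 0.075) | 4.8% | 17.2% (p = 0.0675) | 43.0% (p = 0.06) |
| 95% (p = 0.05) | 82.9% | 94.2% (p = 0.045) | 98.7% (p = 0.04) |

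**Same illustration at full enrolment**

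Inputs: N=1725, attrition hazard −ln(0.48)/5 (52% over 5 years), complication hazard −ln(S)/5 × (1 − f), where S is the true freedom. It was simulated with 8,000 trials per cell and four versions of the bound (log or log-log scale, Peto or Greenwood standard error).

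- True freedom 95%: about 61 events. Rejection is 93–98% with none moved and 99% or more with 10% moved. Apparent freedom goes from 95.0% to 0.95^0.9 = 95.5%.
- True freedom 92.5%: about 92 events. Rejection is 2–6% with none moved and 15–28% with 10% moved. A median of about 17 to 19 events must move before the Peto bound clears 92.5%.

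**The case against.** The strongest reply is that Table 2 is a reporting list and not a sorting rule. Section 6.1 speaks of events that are already unrelated and are then shown in the table. Table 2 also omits infection, bleeding and venous occlusion, which section 11.0 names as possible events, so it cannot be a complete rule. Relatedness is judged first in 5.1.1, 5.2.1 and 11.0; 5.2.2 points to 5.2.1; and no sentence applies Table 2 to the primary endpoint. All of this stands, and on this reading the effect is zero.

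It also stands that the lists in 5.1.1 and 5.2.1 name event types inside a relatedness judgement. The absence of a cause beside each item is not the defect, or the patient-physiology rows would conflict as well. The defect is the narrow phrase in four rows.

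Two stronger inferences are tempting, and the documents support neither:

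- **Insulation damage drops out of the primary endpoint.** Confirmed insulation damage has its own bullet in 5.1.1 and counts there. Only unconfirmed mechanisms are exposed.
- **The primary result is biased.** Nothing shows that Table 2 will be used to classify primary events, and no frequency is given for the exposed group.

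The reply does not remove the conflict of wording. Table 2 is the only place that gives event-specific criteria for unrelated, and its title includes complications. The imaging and electrical adjudication committees in section 19 are described for the sub-study population. A person classifying main-study events could reasonably turn to Table 2.

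**Conclusion.** The inconsistency is real and minor to moderate. Four rows set a test for unrelated that is narrower than the protocol's own test elsewhere, and section 4.2 supplies the counter-example. The size is zero if 5.2.1 is followed. If the four rows are applied as worded, the effect is anti-conservative for the primary endpoint, Table 1, the trend analysis and the final proportions.

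The test decision is at risk only if true freedom lies near 92.5%. At the planned 95% and full enrolment the decision barely changes, and the effect is on the reported rates. Every share used above is an assumption, as are constant hazards and, at full enrolment, attrition independent of complications. Events managed without invasive intervention are observations and do not enter the primary endpoint, except perforations, which section 11.0 always counts as complications.

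**What to change.** In the four Table 2 rows, replace the fracture-or-dislodgement condition with the one that the VT/VF-detection row already uses, namely a cause other than the Optisure RV lead. In 5.1.1 and 6.1, state that a single test applies to the primary endpoint and to all reports: whether the complication is related to the Optisure RV lead, as in 5.2.1 and 11.0. State also that Table 2 is a reporting list only. Leave the patient-physiology rows as they are. The event list should not itself be declared the rule for relatedness, because it carries no cause condition and would then draw in threshold and sensing events due to patient physiology.

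The cost is wording in two sections and four table rows, with no new data. The estimated complication-free rate may come out slightly less favourable.

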6.2 Final Study Report

In addition to the summaries described in section 6.1, the following will also be included in the final report: The number and proportion of patients who experience each type of complication in Table 1 at 5 years will be presented along with the 95% confidence intervals for the proportion based on the Clopper-Pearson exact Binomial method. A Kaplan-Meier analysis will be performed for all-cause death for the final report.

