The expected distribution of ICDs to CRT-Ds in this post-market surveillance study is 3:2³. The annual mortality in the ICD patient population varies between 5.6% and 7%, which are calculated from the published results of the SCD-HeFT and MADIT II trials^{4,5}. Assuming an annual mortality of 7% in the ICD patient population, the mortality at 5 years is 30%. In the recent RHYTHM ICD/QuickSite 1056K left heart lead study⁶, the annual mortality was 12.8%, which gives a mortality of 49% at 5 years. Hence the expected overall mortality in this post-approval study at 5 years is 38% ($=0.6 \times 0.30 + 0.4 \times 0.49$).

3. Withdrawal due to Lost-to-follow-up, system explant due to heart transplant/infection, patient/physician request

In the ongoing St. Jude Medical post-approval study consisting of CRT devices and LV leads⁷, out of a total of 1127 enrollments, 102 patients have been withdrawn for reasons other than death during an average of 22 months of follow-up. This translates to an attrition of 22% over 5 years. It is assumed that attrition in the study over 5 years is 22%. This is a conservative assumption since the CRT Device System Post Approval Surveillance study solely enrolled patients indicated for CRT, while this study is expected to enroll patients receiving either a CRT-D or an ICD.

Assuming that deaths and withdrawals are independent events, the total attrition is thus expected to be approximately 52% ($= 1 - (1 - 0.38) \times (1 - 0.22)$) over 5 years. Thus, a minimum of 1725 patients will be enrolled in the post-approval study.

Patient Group

All patients who give consent for the study and undergo an attempted implant of the Optisure lead or had an Optisure lead implanted within 30 days of enrollment will be included in this analysis.

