16.0 Withdrawals

Withdrawal is defined as termination of participation of a patient from a clinical study. All reasonable efforts should be made to retain the subject in the clinical study until completion of the clinical study. Reasons for withdrawal include, but are not limited to the following:

- Patient Death
- Patient and/or Family Request
- Patient Lost to Follow-Up - Defined as the following: Patient will be considered "lost to follow-up" after a minimum of two documented phone calls were made by personnel at the study center to the patient or emergency contact, a certified letter was sent to the last known address, and two consecutive visits pass without an investigator receiving data
- Patient Non-compliance

- Patient Participation terminated by Investigator
- Sponsor Request
- Unsuccessful Implant
- Heart transplant
- Optisure lead removed or capped without a Optisure lead replacement

A Withdrawal Case Report Form should be completed and submitted to St. Jude Medical using the EDC system. **If there is a potential withdrawal in the study, please contact a member of the study team to see if there is anything that can be done to keep the patient in the study.**

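### Section 6.2 reports crude 5-year complication proportions with exact binomial intervals although 52% of patients are expected to leave before 5 years

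*Protocol*

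**What the plan says.** Section 6.2 adds to the final report the number and "proportion of patients who experience each type of complication in Table 1 at 5 years", "along with the 95% confidence intervals for the proportion based on the Clopper-Pearson exact Binomial method". It names no denominator.

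The denominator has to be taken from section 5.2.1. The patient group there is everyone who consents and has an attempted implant, or who "had an Optisure lead implanted within 30 days of enrollment will be included in this analysis"; no minimum follow-up is required. Table 1 uses one patient count for every row, with the column headed "Number of Patients with Comp (No. of pts = X").

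The same section sets out the expected losses. On mortality: "Hence the expected overall mortality in this post-approval study at 5 years is 38" per cent. A further 22% are expected to leave for other reasons, under the heading "Withdrawal due to Lost-to-follow-up, system explant due to heart transplant/infection, patient/physician request". Combined, "the total attrition is thus expected to be approximately 52" per cent over 5 years.

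Section 5.1.1 handles the same patients differently. The primary endpoint is a Kaplan-Meier estimate with censoring at withdrawal, and section 16.0 lists death as a withdrawal reason. Section 5.1.1 also plans Kaplan-Meier curves for each complication category, and Table 1 includes complications per patient-year.

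**The concern.** A Clopper-Pearson interval presumes a fixed number of patients whose 5-year status is all known. Here about half are expected to have left by then. With all enrolled patients in the denominator, someone who leaves complication-free at month 8 is counted as complication-free at month 60.

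The final report would then hold two 5-year figures for each complication type: a crude proportion and a point on a Kaplan-Meier curve. They would differ systematically, and nothing in the protocol says what each estimates. The crude figure is the lower of the two, and it is the only one by category for which this document specifies an interval. The study exists to characterise chronic lead performance, and late failures are where the gap is widest.

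**Working it through.** **Inputs.** n = 1725, 5-year death 38%, other withdrawal 22% and overall expected complication rate 3.5% (all 5.2.1); exponential event times (5.1.1). The protocol gives no rate by category. An even split of 3.5% over the six Table 1 rows, 3.5/6 = 0.58%, is my assumption for an average category; 1% and 2% stand for larger ones.

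**The plan's own figures.** Attrition: 1 − (1 − 0.38)(1 − 0.22) = 0.5164, stated as 52%. Enrolment: 828/(1 − 0.52) = 1725. Both reproduce.

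**Hazards per year.**
- Death: d = −ln(0.62)/5 = 0.0956
- Other withdrawal: w = −ln(0.78)/5 = 0.0497
- Sum: m = 0.1453

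**Expected crude proportion.** For complication hazard λ it is λ/(λ+m) × [1 − exp(−5(λ+m))]. There are two possible targets:
- Net (Kaplan-Meier) risk p, with λ = −ln(1 − p)/5.
- Cumulative incidence p with death competing, with λ solved from λ/(λ+d) × [1 − exp(−5(λ+d))] = p.

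Coverage is the Binomial(1725, crude) probability of a count whose 95% Clopper-Pearson interval contains p.

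| True 5-year p | Crude, net target | Coverage | Crude, cumulative-incidence target | Coverage |
|---|---|---|---|---|
| 0.58% | 0.415% | 92.6% | 0.522% | 97.4% |
| 1% | 0.711% | 78.1% | 0.894% | 93.9% |
| 2% | 1.423% | 57.2% | 1.789% | 91.0% |

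The relative bias hardly depends on p: about −29% against net risk and about −11% against cumulative incidence.

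**How much of the 22% is true loss.** The −11% treats all other withdrawals as patients still at risk. The protocol mixes transplant and infection explants into the 22% and gives no split. If only 5, 10 or 15 points are true loss and the rest compete like death (assumption), the bias against cumulative incidence is −2.2%, −4.6% or −7.0%. Coverage at 2% is then 95.1%, 94.6% or 93.5%.

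**Event timing** (Weibull shape, assumed; net target / cumulative-incidence target):
- Early events, shape 0.5: bias −20% / −7%; coverage 96% / 98% at 0.58% and 79% / 94% at 2%.
- Late events, shape 2: bias −37% / −15%; coverage 87% / 97% at 0.58% and 33% / 87% at 2%.

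**Alternative denominator: patients with an event plus 5-year completers.** At net 0.58%, expected events are 1725 × 0.00415 = 7.2 and complication-free completers are 1725 × 0.4836 × 0.9942 = 829. The ratio 7.2/(7.2 + 829) is 0.86%, so this reading is biased upward.

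**The case against.** The strongest reply is that most of the 29% is a choice of target and not an error. Under constant hazards, cumulative incidence with death competing is itself about 20% below the Kaplan-Meier risk (for a net risk of 1% it is 0.795%), because a patient who dies can no longer have a lead complication. On that target, counting deaths as event-free is correct. What is left is bias from other withdrawals, at most 11% with constant hazards. It is smaller in practice because some of those patients are no longer at risk: transplant and infection explants are in the 22%, and section 16.0 also withdraws patients with "Optisure lead removed or capped without a Optisure lead replacement". This stands, and only the smaller figure is bias under either target. But 6.2 does not name cumulative incidence as its target, and the protocol plans no such analysis.

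A second reply is that the denominator is inferred. The inflation 828/0.48 suggests that 828 five-year completers were the intended base, and exact denominators are often left to a statistical analysis plan, which is not at hand. It is true that the direction of the error depends on this. The stated patient group and Table 1 favour all enrolled patients, however, and the event-or-completer reading is also wrong (0.86% for 0.58%). The interval method is fixed in the protocol itself, and neither reading makes it valid.

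Third, the endpoint is secondary with no decision rule, category Kaplan-Meier curves and rates per patient-year are planned, and an average category keeps near-nominal coverage. All of this stands and limits the weight of the point. It does not remove the bias in the point estimates, or the absence in this document of an interval for anything but the crude proportion.

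**Conclusion.** The concern holds and should be fixed; it is not critical. With all enrolled patients as denominator, constant hazards and the protocol's own attrition, the section 6.2 proportions are about 29% low against the Kaplan-Meier risk used for the primary. They are about 11% low against cumulative incidence with death competing, or 2% to 7% low if only 5 to 15 of the 22 withdrawal points are true loss. In absolute terms an average category of 0.58% would be reported as 0.42% or 0.52%. Serious loss of coverage arises only for a dominant category, mainly against the net risk and mainly with late events. The primary test and its power are untouched.

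**What to change.** In sections 5.2.1 and 6.2, estimate the 5-year rates, overall and by Table 1 category, either as 1 minus Kaplan-Meier (consistent with the primary) or as cumulative incidence with death competing. State which one, and give matching two-sided 95% intervals, for example on the log-log scale. Keep the crude counts and percentages as descriptive, and do not label them as 5-year figures.

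In 3,000 simulated studies per setting under constant hazards, both replacements were unbiased at 0.58%, 1% and 2%. Coverage was 96.1%, 95.5% and 94.6% for 1 minus Kaplan-Meier, and 96.1%, 95.6% and 95.2% for cumulative incidence.

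The change is to analysis wording only. It needs no extra patients or data, and the category Kaplan-Meier curves are already planned. The price is less favourable figures: at 0.58% the mean upper limit rises from 0.84% to 1.22% (1 minus Kaplan-Meier) or from 0.98% to 1.11% (cumulative incidence).
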